The study will not be commenced without the prior written approval of a properly constituted Institutional Review Board / Independent Ethics Committee (IRB/IEC). No changes will be made to the study protocol without the prior written approval of the Sponsor or their designee and the IRB/IEC, except where necessary to eliminate an immediate hazard to the patients.

I have read and understood and do agree to abide by all the conditions and instructions contained in this protocol.

Signature (Principal Investigator)

Date

Printed Name

PROTOCOL SYNOPSIS

| | |
|-----------------------|--|
| Sponsor: | Laboratorios Salvat, S.A. |
| EudraCT number | 2019-003463-22 |
| Title: | A Phase III, Multicenter, Randomized, Double-Blind Clinical Trial to Assess the Efficacy and Safety of Clotrimazole 1% Otic Solution Compared to Placebo for the Treatment of Fungal Otitis Externa (Otomycosis). |
| Short title: | Clotrimazole 1% Otic Solution for the Treatment of Otomycosis. |
| Acronym | CLEAR-2 |
| Study Number: | CLOTOT3-16IA03 |
| Study Phase: | III |
| Study Centers: | Multi-center study in approximately 17 sites (Bulgaria, Portugal, Romania and Spain). |
| Study Period | Planned duration of the study (for each patient): 4 weeks Planned recruitment period: 12 months |
| Objectives: | To evaluate the efficacy and safety of topical Clotrimazole 1% otic solution for the treatment of otomycosis. The main efficacy endpoint is proportion of subjects with therapeutic cure (mycological cure and clinical cure) at test-of-cure in MITT population. Mycological cure is defined as eradication (culture does not show growth of any fungal pathogen) or presumed eradication (there is no material to culture and overall clinical outcome is clinical cure). Clinical cure is defined as a total sign/symptoms score (TSSS) of zero on the 4-point severity scale for pruritus, otalgia, ear fullness and otorrhea. |
| Study Design: | Multicenter, Randomized, 2-arm parallel-group, double blind, placebo-controlled study in patients suffering from Fungal Otitis Externa (Otomycosis). This study will compare the efficacy and safety of Clotrimazole 1% otic solution to that of Placebo, when administering one vial twice daily during 14 days. |

| | |
|---|--|
| Study medication, Dosage, and Route of Administration: | 
Test product: 1 vial of Clotrimazole 1% otic solution in the affected ear(s) twice a day during 14 days.
 
Reference product (placebo): 1 vial of Saline solution 0.9% in the affected ear(s) twice a day during 14 days.
 
A patient study medication kit will contain 6 pouches with 1 strip of 5 vials in each pouch, for a total of 30 vials. Patients with bilateral otomycosis will receive 2 kits with the same treatment. A study staff member will remove 2 vials from the kit and keep them for traceability (if bilateral, remove 2 vials from each kit). The remaining 28 vials will be returned to the kit for dispensation to the patient. The first administration will be at the study site supervised by a study staff member.
 
The solution will be warmed by holding the vial for one or two minutes to avoid dizziness which may result from the instillation of a cold solution. The patient will lie with the affected ear upward and 1 vial of the otic solution will be instilled in the ear canal. The patient must remain in the position for 1 minute. Repeat, if necessary, for the opposite ear.
 |
| Patient Population: | 
Patients of 18 years of age and older, with otomycosis.
 
A total of 191 patients will be randomized in a 2:1 ratio (Clotrimazole 1% otic solution: Placebo) to obtain 150 evaluable patients (100 Clotrimazole 1% and 50 Placebo)
 |
| Study Rationale: | 
Clotrimazole is a broad spectrum antifungal agent that was found to effectively controls fungal isolates attributed to otomycosis (Aspergillus and Candida) when administered as 1% otic solution twice daily. Each dose consists of approximately 1.7 mg of clotrimazole. The dosing regimen has been shown to be effective in the treatment of otomycosis leading to a negative mycological culture and near total suppression of clinical signs/symptoms (pruritus, otorrhea, ear fullness and otalgia).
 
Subjects of 18 years of age and older, with otomycosis will be randomized in a 2:1 ratio to receive treatment with Clotrimazole 1% otic solution or placebo (Saline solution 0.9%). Subjects will be administered one vial of Clotrimazole 1% otic solution or placebo twice daily for 14 days.
 |

| | |
|------------------------------|--|
| Eligibility Criteria: | Inclusion Criteria: 
 • At least 18 years of age at Visit 1 (Day 1, Screening/Baseline). • Clinical diagnosis of fungal otitis externa (otomycosis) in one or both ears, where topical treatment is indicated. • Presence of at least two of the following symptoms at baseline: pruritus, otalgia and ear fullness. • Presence of debris and/or drainage clinically consistent with a fungal infection, i.e. white or black appearance consistent with Aspergillus spp. or Candida spp. • Otorrhea/debris sample for bacterial and mycological cultures. • Provide written informed consent. • Willing and able to follow all instructions and attend all study visits. • Females who are not pregnant, not lactating and are not planning a pregnancy during the study. All females of childbearing potential will be able to participate only if they have a negative urine pregnancy test at baseline and if they agree to use adequate birth control methods to prevent pregnancy throughout the study. |
| | Exclusion Criteria: 
 • Known bacterial otitis externa or malignant otitis externa. • Tympanic perforation, tympanostomy tubes inserted and post mastoid surgery. • Structural ear anomalies which may difficult the evaluation of the therapeutic response. • Uncontrolled diabetes mellitus. • Known or suspected hypersensitivity to clotrimazole or any component of study medication. • History of an immunosuppressive disorder and/or current immunosuppressive therapy. • History of other disease, metabolic dysfunction, physical examination finding, or clinical laboratory finding giving reasonable suspicion of a disease condition that contraindicates the use of an investigational drug, might affect the interpretation of the results of the study, or renders the subject at high risk for treatment complications. • Any recent systemic infection within 30 days of the inclusion or any current infection requiring systemic antimicrobial or systemic antifungal therapy. |

| | |
|--|--|
| | 
• Use of topical therapy with antifungal properties in the target ear within 2 weeks of the inclusion.• Use of systemic antifungal therapy within 1 month of the inclusion.• Concurrent use of any compound, agent or substance that is applied or instilled to the evaluable ear or surrounding area, except non-bacteriostatic saline solution for potential additional cleaning before taking the sample to be cultured.• Concurrent use of analgesic therapy (prescription or over the counter) with anti-inflammatory properties (acetylsalicylic acid for cardiovascular prevention at doses of 325mg or less is allowed). Analgesics without anti-inflammatory properties, such as acetaminophen and anti-inflammatory agents at stable doses at least 30 days prior to enrollment are allowed.• Concurrent use of non-topical antipruritics, except antihistamines at stable doses (at least 30 days prior to enrollment).• Concurrent use of any systemic corticosteroid, except nasal or inhaled corticosteroids at stable doses (at least 30 days prior to enrollment).• Prior participation in this trial unless patient was not randomized.• Participation in other investigational drug or device clinical trials within 30 days prior to the inclusion, or planning to participate in other investigational drug or device clinical trials within 24 days of starting treatment with study medication. |
|--|--|

| | |
|--------------------------|--|
| Study Evaluation: | 
Visit 1 (Baseline; Day 1)
 
 • Informed Consent. • Collection of general patient information: Medical History. • Physical examination (including Ear examination with or without microscope). • Vital signs examination (Temperature, blood pressure and pulse). • Collection of urine for pregnancy test, if the subject is a woman of childbearing potential. • Clinical assessment: 
 ○ Examination of both ears. ○ Evaluation of signs and symptoms: 
 - Pruritus - Otalgia - Ear fullness - Otorrhea • Collection of otorrhea/debris sample for bacterial and mycological cultures. • If bilateral otomycosis is present on exam, culture specimen collection should be performed only on the evaluable ear. • Debridement of the ear(s) (after collection of the culture specimen). • Randomization. • Dispensing study medication and administration of first dose. • Adverse Events Assessment. • Concomitant medication use. • Provide a visit calendar. 
Visit 2 (During treatment; Day 8-10)
 
 • Vital signs examination (Temperature, blood pressure and pulse). • Clinical assessment: 
 ○ Examination of both ears. ○ Evaluation of signs and symptoms: 
 - Pruritus - Otalgia - Ear fullness |
|--------------------------|--|

| | |
|--|---|
| | 
 - Otorrhea ○ Overall clinical outcome, based on sum of signs and symptoms scores (resolved, improved, not changed, worsened). ● Collection of otorrhea/debris sample (if present) for bacterial and mycological cultures. ● Debridement of the ear(s), if applicable (after collection of the culture specimen). ● Adverse Events Assessment. ● Concomitant medication. 
In the case of patients who report no improvement in otomycosis signs/symptoms, the Investigator will choose one of the two following options for the patient:
 
 1. Continue with the study medication and attend Visit 3. 2. Discontinue study medication. The Investigator may treat patient with other medication (rescue medication) at their discretion. 
 ○ If investigator prescribes rescue medication, the patient will be withdrawn from the study. The clinical outcome for the patient will be recorded as Treatment failure at the End of Study form. ○ If investigator does not prescribe any rescue medication, the patient will be expected to return for a clinical and safety evaluation at Visit 3. 
Visit 3 (End of Treatment; Day 15-17) (EOT)
 
 ● Vital signs examination (Temperature, blood pressure and pulse). ● Clinical assessment: 
 ○ Examination of both ears ○ Evaluation of signs and symptoms: 
 - Pruritus - Otalgia - Ear fullness - Otorrhea ○ Overall clinical outcome, based on sum of signs and symptoms scores (resolved, improved, not changed, worsened). ● Collection of otorrhea/debris sample (if present) for bacterial and mycological cultures. |
|--|---|

| | |
|------------------------------|---|
| | 
 • Debridement of the ear(s), if applicable (after collection of the culture specimen). • Adverse Events Assessment. • Concomitant medication use. • Collection of remaining study medication and evaluation of compliance. 
In the case of patients who report no improvement in otomycosis signs/symptoms, the Investigator will choose one of the two following options for the patient:
 
 1. Continue the patient in the study without any treatment for otomycosis (rescue medication) until Visit4. The patient will come to Visit 4. 2. Prescribe rescue medication and withdraw the patient from the study. The Investigator will withdraw the patient from the study and will treat patient with other medication at their discretion. The clinical outcome for the patient will be recorded as Treatment Failure at the End of Study form. 
Visit 4 (Test of Cure; Day 24-26) (TOC)
 
 • Vital signs examination (Temperature, blood pressure and pulse). • Clinical assessment: 
 ○ Examination of both ears ○ Evaluation of signs and symptoms: 
 - Pruritus - Otalgia - Ear fullness - Otorrhea ○ Overall clinical outcome, based on sum of signs and symptoms scores (resolved, improved, not changed, worsened). • Collection of otorrhea sample (if present) for bacterial and mycological cultures. • Debridement of the ear(s), if applicable (after collection of the culture specimen). • Adverse Events Assessment. • Concomitant medication. • Completion of the end of study form. |
| Efficacy Assessments: | Efficacy: Efficacy will be assessed by mycological assessment (fungal culture), AND the sum of signs and |

| | |
|-------------------------------------|--|
| | 
symptom scores (pruritus, otalgia, ear fullness and otorrhea).
 
Primary endpoint:
 
 Therapeutic cure at test-of-cure (Visit 4) in the MITT population. 
Therapeutic cure is defined as both mycological cure AND clinical cure.
 
Mycological cure is defined as eradication (culture does not show growth of any fungal pathogen) or presumed eradication (there is no material to culture and the overall clinical outcome is clinical cure).
 
Clinical cure is defined as a total signs/symptoms score (TSSS) of zero on a 4-point scale for pruritus, otalgia, ear fullness and otorrhea.
 
No Response is defined as :
 
 a positive fungal culture OR sum of signs and symptoms >0. 
Secondary endpoints:
 
 Overall clinical outcome at Visits 2, 3 and 4. Mycological outcome at Visits 2, 3 and 4. Therapeutic cure at Visit 2 and 3. Changes in TSSS at Visits 2, 3 and 4. Changes in individual signs and symptoms at Visits 2, 3 and 4. 
In the case of bilateral otomycosis the non-selected ear will also be treated and assessed for its clinical evolution.
 |
| Safety Assessments: | 
The safety assessments will include adverse events (AEs), and vital signs. All safety data will be summarized separately. Adverse events will be coded and tabulated by system/organ class and preferred term using the latest version of the Medical Dictionary for Regulatory Activities (MedDRA). Adverse events will be summarized by relationship to treatment and severity. In addition, serious adverse events (SAEs) and AEs leading to discontinuation will be summarized similarly.
 |
| Study Medication Compliance: | 
Compliance will be assessed by a review of the number of vials returned. The number of doses the patient actually took during the treatment period will be divided by the number of doses the patient was expected to take during that period. The resulting ratio will be multiplied by 100% to determine percent compliance. Patients will be considered "compliant" if their percent compliance is between 80% and 100%.
 |

| | |
|-----------------------------|---|
| Statistical Methods: | 
Analysis will include the following populations:
 
• CITT Population (clinical intent-to-treat): includes all randomized subjects.• Safety Population includes all randomized subjects who received at least one dose of the study treatment.• MITT Population (mycological intent-to-treat): includes all randomized subjects who had a positive baseline fungal culture.• MPP Population (mycological per protocol): includes all randomized subjects who had a positive baseline fungal culture, were compliant with the assigned study treatment, and completed the evaluation at the test-of-cure (evaluation phase) within the designated visit window and have no major protocol violations. 
All efficacy analyses performed on the MITT population will be repeated on the MPP population.
 
Sample size calculation:
 
Clotrimazole otic solution should be statistically superior to the placebo ($p<0.05$) with regard to the therapeutic cure at the test-of-cure visit, using the MITT population.
 
Assuming a significance level of 5% and a desired statistical power of 95%, a placebo effect of 30%, and a 2:1 allocation schedule, the total number of patients needed to detect a difference of 30% in the therapeutic cure (100% relative increase) is 150 (100 with clotrimazole and 50 with placebo). The suspected dropout rate due to negative mycological culture at baseline is 21% that leads to a required inclusion of 191 patients (127 for the clotrimazole group and 64 patients for the placebo group).
 
As this is a twin trial if the CLEAR-1 study is completed before this study (CLEAR-2) an updated sample size computation will be performed for CLEAR-2 utilizing the results from the CLEAR-1 given the results from the CLEAR-1 will provide a more accurate estimation of the cure rate for treatment and control arms.”
 |
|-----------------------------|---|

TABLE OF CONTENTS

| | |
|---|-----------|
| 1. INVESTIGATORS AND STUDY ADMINISTRATIVE STRUCTURE | 16 |
| 2. INTRODUCTION..... | 17 |
| 2.1 Background..... | 17 |
| 2.2 Rationale for the Study | 19 |
| 2.3 Risk-Benefit Assessment..... | 19 |
| 3. OBJECTIVES | 21 |
| 3.1 Primary Objective | 21 |
| 3.2 Secondary Objectives..... | 21 |
| 4. OVERALL DESIGN AND PLAN OF THE STUDY..... | 22 |
| 4.1 Overview | 22 |
| 4.2 Justification for Study Design | 25 |
| 5. STUDY POPULATION..... | 26 |
| 5.1 Inclusion Criteria | 26 |
| 5.2 Exclusion Criteria | 26 |

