7.1.1.4 Otorrhea

Otorrhea in both ears will be assessed by the investigator at all visits. For consistency, the same individual should perform all the assessments at all visits, if possible. Otorrhea will be assessed as:

- Severe (3): copious discharge that prevents visualization of the tympanic membrane unless the fluid is suctioned
- Moderate (2): the anterior sulcus is full, but the tympanic membrane is still clearly visible
- Mild (1): little fluid accumulating in the anterior tympanomeatal sulcus but the tympanic membrane is still visible
- Absent (0) absence of fluid

At Visits 2, 3 and 4, otorrhea will be considered resolved if the level is 0. Otorrhea will be considered improved if the level is lower than the previous otorrhea assessment.

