8. STUDY CONDUCT

8.1 Schedule of Observations

A schedule of observations and assessments to be performed during the study is provided in Table 1.

Table 1 Schedule of Observations

| Evaluation | Visit 1 Screening (Study Entry) | Visit 2 On treatment | Visit 3 End of Treatment | Visit 4 Post- Treatment Follow-Up |
|---|--|----------------------------|--------------------------------|--|
| Study Day | 1 | 8-10 | 15-17 | 24-26 |
| Informed Consent | X | | | |
| Inclusion/exclusion criteria | X | | | |
| Medical history | X | | | |
| Concurrent symptoms/conditions | X | | | |
| Urine pregnancy test ^a | X | | | |
| Physical examination ^b | X | | | |
| Vital signs ^c | X | X | X | X |
| Pruritus | X | X | X | X |
| Otalgia | X | X | X | X |
| Ear fullness | X | X | X | X |
| Ototorrhoea | X | X | X | X |
| Overall Clinical Outcome | | X | X | X |
| Bacterial and Mycological cultures of ear discharge | X | X ^d | X ^d | X ^d |
| Debridement of the ear | X | X ^d | X ^d | X ^d |
| Randomization through IWRS | X | | | |
| Dispense study medication and explain its use | X | X ^e | | |
| Provide a visit calendar | X | | | |
| Collect used and unused study medication containers | | | X ^f | |
| Concomitant medications | X | X | X | X |
| Adverse events | X | X | X | X |

^a For female patients of childbearing potential.

^b To include a directed examination of the ears, head, nose and oropharynx.

^c To include temperature, blood pressure, and pulse rate.

^d If no discharge (ototorrhoea or debris) is present, no attempt to culture will be made.

^e If patient with unilateral otomycosis at baseline becomes bilateral prior to Visit 3 a resupply study medication kit (with the same medication) will be dispensed for the non-evaluable ear.

^f If patients forget to bring in containers at this visit, they must bring them in no later than Visit 4.

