Used and unused study medication containers will be collected from the patient by a member of the study staff.

In the case of patients with a TSSS greater than 2 on a 4-point scale, the Investigator will choose one of the two following options for the patient:

1. Continue the patient in the study (without receiving any further treatment for the signs/symptoms of otomycosis). The patient will come to Visit 4.
2. Prescribe rescue medication and withdraw the patient from study.

The clinical outcome for the patient will be recorded as Treatment failure at the End of Study form.

8.2.4 Visit 4

Visit 4 will take place on Day 24-26. A member of study staff will contact the patient on the previous days to remind the patient to attend this visit.

Adverse events and concomitant medications will be recorded and vital signs will be assessed.

Pruritus, otalgia, ear fullness and otorrhea will be evaluated as described in Sections 7.1.1.1, 7.1.1.2, 7.1.1.3 and 7.1.1.4. Overall Clinical Outcome will be evaluated by the Investigator as described in Section 7.1.1.5. A sample of ear discharge will be obtained for mycological culture as described in Section 7.1.2 prior to the debridement of the ear.

If the patient took rescue medication (see section 6.7.2) prior to this visit, the patient will be considered Treatment Failure, and no further ear discharge sample will be collected for study purposes.

Upon completing Visit 4, the patient will have completed his or her participation in the study.

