## 2 STUDY OVERVIEW

### 2.1 Study Objectives

#### 2.1.1 Primary Objective

To demonstrate the superior efficacy of Clotrimazole vs. placebo in the treatment of otomycosis, with respect to the therapeutic cure at test-of-cure (TOC; Visit 4) in the mycological intent-to-treat (MITT) population.

**Therapeutic cure** is defined as both mycological cure AND clinical cure.

**Mycological cure** is defined as eradication (culture does not show growth of any fungal pathogen) or presumed eradication (there is no material to culture and the overall clinical outcome is clinical cure)

**Clinical cure** is defined as a total signs/symptoms score (TSSS) of zero on a 4-point scale for pruritus, otalgia, ear fullness and otorrhea.

No Response is defined as:

- a positive fungal culture (i.e., identification of a fungal pathogen from fungal and/or bacterial cultures) OR
- sum of signs and symptoms  $>0$  on TOC

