**Table 1 Schedule of Observations**

Evaluation	Visit 1 Screening (Study Entry)	Visit 2 On treatment	Visit 3 End of Treatment	Visit 4 Test of cure
Study Day	1	8-10	15-17	24-26
Informed Consent	X			
Inclusion/exclusion criteria	X			
Medical history	X			
Concurrent symptoms/conditions	X			
Urine pregnancy test a	X			
Physical examination b	X			
Vital signs c	X	X	X	X
Pruritus	X	X	X	X
Otalgia	X	X	X	X
Ear fullness	X	X	X	X
Otorrhea	X	X	X	X
Overall Clinical Outcome		X	X	X
Bacterial and Mycological cultures of ear discharge	X	X d	X d	X d
Debridement of the ear	X	X d	X d	X d
Randomization through IWRS	X			
Dispense study medication and explain its use	X	X e		
Provide a visit calendar	X			
Collect used and unused study medication containers			X f	
Concomitant medications	X	X	X	X
Adverse events	X	X	X	X

a For female patients of childbearing potential.

b To include a directed examination of the ears, head, nose and oropharynx.

c To include temperature, blood pressure, and pulse rate.

d If no discharge (otorrhea or debris) is present, no attempt to culture will be made.

e If patient with unilateral otomycosis at baseline becomes bilateral prior to Visit 3 a resupply study medication kit (with the same medication) will be dispensed for the non-evaluable ear.

f If patients forget to bring in containers at this visit, they must bring them in no later than Visit 4.

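### The Visit 4 sampling instructions conflict on debris and on bacterial culture; followed literally, the synopsis line would reduce therapeutic cure to clinical cure

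*Protocol*

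**What the plan says.** **Which material is sampled at Visit 4.** The protocol synopsis (Study Evaluation) gives the Visit 4 sample as "Collection of otorrhea sample (if present) for bacterial and mycological cultures". For Visits 2 and 3 the same list has "Collection of otorrhea/debris sample (if present) for bacterial and mycological cultures", and its Visit 1 line also names debris. Table 1 footnote d, which governs Visits 2 to 4, treats either material as discharge; in the SAP it reads "If no discharge (otorrhea or debris) is present, no attempt to culture will be made", and the protocol's footnote has the same content. Protocol Section 4.1 explains ear exudate as otorrhea, or debris where there is no otorrhea, and has exudate collected at Visits 3 and 4. Section 7.1.2.1 also refers to a combined otorrhea/debris sample.

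**Which cultures are done at Visit 4.** Section 8.2.4 says "A sample of ear discharge will be obtained for mycological culture as described in Section 7.1.2 prior to the debridement of the ear". Sections 8.2.2 and 8.2.3, for Visits 2 and 3, name both cultures. For Visit 4, so do the synopsis, Section 4.1 and the Table 1 row "Bacterial and Mycological cultures of ear discharge". SAP Section 2.1.1 defines a positive fungal culture at test of cure as "identification of a fungal pathogen from fungal and/or bacterial cultures".

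**How this enters the endpoint.** Clinical cure is TSSS = 0 over pruritus, otalgia, ear fullness and otorrhea. The zero level for otorrhea (Section 7.1.1.4) is "Absent (0) absence of fluid". A clinically cured patient with nothing to culture is a presumed eradication, which counts as mycological cure.

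**The concern.** Debris is an entry requirement (inclusion criterion 4) but is not scored in the TSSS. In a patient whose ear canal is dry and free of symptoms, culturing debris is the only way that remaining fungus can count against cure. If debris is left out at Visit 4, the culture can no longer change any patient's primary outcome.

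The omission of bacterial culture in Section 8.2.4 is a separate conflict, but it touches the same endpoint. The SAP accepts a fungal pathogen found in the bacterial culture as a positive result, and that route closes if no bacterial culture is done.

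Both conflicts fall at the visit that decides the primary endpoint, in a trial planned for about 17 sites in four countries.

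**Working it through.** **1. Places side by side (Visit 4)**

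| Place | Material | Cultures |
|---|---|---|
| Protocol synopsis | otorrhea only | bacterial and mycological |
| Protocol 4.1 | exudate (otorrhea, else debris) | bacterial and mycological |
| Table 1 and footnote d, protocol and SAP | otorrhea or debris | bacterial and mycological |
| Protocol 7.1.2.1 | otorrhea/debris | fungal and bacterial species identified |
| Protocol 8.2.4 | ear discharge, with reference to 7.1.2 | mycological only |

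The synopsis is the outlier on material and Section 8.2.4 is the outlier on cultures.

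**2. Consequence of the synopsis line taken literally**

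Four items scored 0 to 3 give 4^4 = 256 score patterns. One has TSSS = 0, and in it otorrhea is 0. So none of the clinically cured patterns can yield an otorrhea sample. Every clinically cured patient becomes a presumed eradication, and therapeutic cure equals clinical cure. Under footnote d, a clinically cured patient with debris is cultured and can still fail.

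**3. What the SAP does with a clinically cured patient whose debris was not sampled**

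SAP 2.3.1.2.1 covers samples not taken or not shipped only under Presumed Persistence, which requires that the patient is not clinically cured. Two readings remain:

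- If absence of material means no otorrhea, the patient is a presumed eradication, hence a success.
- If debris counts as material, no named category fits. The outcome is Indeterminate, hence a failure under SAP 3.1.3 and 3.4.1.

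The same patient can therefore be a success or a failure on the primary endpoint.

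**4. The plan's own figures**

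Inputs (protocol 10.1.1 and 10.1.10.1): 30% versus 60%, two-sided 5%, 50 placebo and 100 clotrimazole patients.

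Pooled rate = (50×0.30 + 100×0.60)/150 = 0.50. Null SE = √(0.25×(1/50 + 1/100)) = 0.0866. Alternative SE = √(0.21/50 + 0.24/100) = 0.0812.

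Power = Φ[(0.30 − 1.96×0.0866)/0.0812] = Φ(1.60) = 94.6%, against a stated 95%. Inflation: 100/0.79 → 127 and 50/0.79 → 64, total 191. The sample size reproduces, and this point does not affect it.

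**5. Illustration of size (assumed rates; none is in the documents)**

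Let r be the share of clinically cured patients with culture-positive debris: 10–30% on placebo and 5–10% on clotrimazole.

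*(a) The planned 30% and 60% are what otorrhea-only sampling would report.* Culturing debris gives 0.30×(1 − r_p) and 0.60×(1 − r_c):

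| r_p, r_c | Placebo | Clotrimazole | Difference |
|---|---|---|---|
| 10%, 5% | 27% | 57% | 30 |
| 10%, 10% | 27% | 54% | 27 |
| 30%, 5% | 21% | 57% | 36 |
| 30%, 10% | 21% | 54% | 33 |

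In patients, 1.5 to 4.5 of 15 placebo cures and 3 to 6 of 60 clotrimazole cures would be reclassified. The difference is 30 + 30r_p − 60r_c points. It exceeds 30 only if r_p is more than twice r_c.

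*(b) The planned 30% and 60% are therapeutic cure rates with debris cultured, as the protocol labels them.* Otorrhea-only sampling would report 0.30/(1 − r_p) and 0.60/(1 − r_c). Over the same ranges the extremes are 42.9% versus 63.2% (20.3 points, power 65.8%) and 33.3% versus 66.7% (33.3 points, power 97.8%).

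Both calculations span 30 points, so the direction is not determined.

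**The case against.** The strongest reply is that these are two dropped words. Footnote d appears in both documents, Sections 4.1 and 7.1.2.1 keep debris, and Section 8.2.4 itself refers to Section 7.1.2. The protocol also uses otorrhea loosely: for Visit 2, Section 4.1 speaks of an otorrhea sample where the synopsis has otorrhea or debris. Sites receive sampling kits with standardized instructions in a laboratory manual that is not among these documents, and they are trained on procedures.

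This stands as an account of intent, and loose drafting is the likely explanation. It does not remove the conflict, because a visit-by-visit list still gives a different instruction at the primary endpoint visit. Nor does the SAP define absence of material in a way that settles the coding.

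A reader might infer more than the documents support:

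- *That clinically cured patients are never cultured.* They are sampled at Visit 1, and at Visits 2 and 3 if material is present. The gap concerns Visit 4 only.
- *That patients enter the MITT population on two cultures and are cleared on one.* The SAP sentence accepting either culture sits in the definition of no response at test of cure. The MITT definition asks for a positive baseline fungal culture and does not mention bacterial cultures.
- *That sites measured different endpoints.* Nothing in the documents shows which page the sites followed.

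**Conclusion.** Wrong as written: an internal inconsistency in the sampling rule for the primary endpoint visit. The two conflicts follow from the text alone. The collapse of therapeutic cure into clinical cure is conditional on a site following the synopsis line literally. It would be too strong to say that the mycological component of the primary endpoint is empty in the plan as a whole, because every other place keeps debris. Mycological outcome as a secondary endpoint also keeps its content, since patients with otorrhea are still cultured.

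Under the literal reading, 0% of clinically cured patients are cultured at Visit 4. The effect on the treatment difference cannot be sized from the documents. The range of 27 to 36 points rests entirely on assumed debris rates and on taking 30% and 60% as clinical cure rates, so a claim of bias in either direction is not supported. The effect of omitting bacterial culture cannot be sized either, because the documents do not say how often it finds fungus that the fungal culture misses.

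**What to change.** Reconcile the passages to Table 1:

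- **Protocol synopsis, Visit 4:** add debris, so that the line matches those for Visits 2 and 3.
- **Protocol Section 8.2.4:** name bacterial as well as mycological culture, as Sections 8.2.2 and 8.2.3 do.
- **Protocol Section 7.1.2.1 and SAP Section 2.3.1.2.1:** state that absence of material means neither otorrhea nor debris in the evaluable ear, including when TSSS = 0. A clinically cured patient with unsampled debris is then not coded as a presumed eradication. Under the SAP's existing rules the outcome becomes Indeterminate and counts as a failure; the SAP should say so explicitly.

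The cost is a few changes of wording and a reminder to sites. Table 1 already schedules both cultures at Visit 4, and the kits and central laboratory are already provided for. The small downside is that reported cure rates may be slightly lower in both arms than under otorrhea-only sampling.
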